### **4.2. General Outline**

Children, 2-10 years of age will be invited to participate. The original study site is Mott Children's Health Center (MCHC) in Genesee County, Michigan. Following a slow recruitment period, the University of Michigan School of Dentistry (UMSOD) Children's Clinic was added as a second study site. Given the current data in the literature, the combined failure rate for conventional restorative techniques (e.g. compomers) is approximately 29% at one year follow-up, while application of silver diamine fluoride has a failure rate of 63% at one year follow-up, with increased success over time. Although the failure rate of SDF at one-year follow-up seems alarming, as indicated by Zhi, *et al.* it may be possible to increase the success rate with additional applications providing success rates up to 90.1% at 24 months. Using these data,  $\alpha$ -value of 0.05 and a Power set at 80%, the resulting sample size would be 68 (34 per group) as calculated using the software, nQuery (Appendix 1). To account for 30% attrition, the final number needed for the initial study will be 98 (92 for 25% attrition, 86 for 20% attrition). Subjects will be contacted by phone regularly and invited to two intermediate clinic visits (plus a final study visit) to reduce attrition (Table 1). Given a review of the current literature of the few Randomized Controlled Clinical Trials involving SDF worldwide, the majority of this research has been completed with pre-school aged children. Almost all research discusses arresting or prevention of caries in the

primary dentition, as well as prevention of caries on first permanent molars. Due to the strength of the current research, this study will be focused on the primary dentition of children in the U.S. These children and their parents will be approached when presenting for examination/recall/or treatment at Mott Children's Health Center, Flint, MI, or the University of Michigan School of Dentistry Children's Clinic, Ann Arbor, MI. Interested families with children that qualify following screening examination will be provided with an *Informed Consent/Assent* (Appendix 3) and an *Enrollment Information Form* (Appendix 4).

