## 6. Study Visits and Intermediate Contacts

Recalls for both groups will occur via phone questionnaire as well as follow-up visits. Participants will be contacted at 1 month, 2 months, 4.5 months and 9 months ( $\pm$  2 weeks) following restoration placement or application of SDF. Subjects will need to present to the clinic for follow-up visits at 3 months ( $\pm$  6 weeks), 6 months ( $\pm$  6 weeks), and for study completion at 12 months ( $\pm$  6 weeks) (Table 1). Subjects will also be called to schedule and confirm these follow-up visits; these short calls will require no payment to the study subjects. In the case of an emergency, an emergency visit will be scheduled at Mott Children's Health Center or the University of Michigan School of Dentistry. An emergency will be evaluated and treated according to the AAPD guidelines, followed by completion of appropriate case report forms (CRFs) and reporting to IRBs and study sponsors (Appendix 10, CRF 14-17). In the event of minor or major failure in either study group, the subject will be withdrawn from the study and teeth will be given the appropriate treatment as stated in the AAPD Guidelines free of charge, these teeth will be categorized as a failure, and a *CRF 04 Treatment Deviation CRF (Appendix 10, CRF 04)* will be completed.

**Table 1.** Patient Contact Interval

Patient Contact	Recall Interaction	Time Scale
Clinic Visit #1	Consent/Accent, baseline questionnaires, initial caries assessment, radiographs*, intervention	T = 0
Intermediate Contact	Attrition prevention, update contact information, follow-up on pain	T = 1 month, 2 months (Additional reminder for Clinical Visit #2)
Clinic Visit #2	Assessment for major and minor failure & assessment of pain and parent satisfaction	T = 3 months
Intermediate Contact	Attrition prevention, update contact information, follow-up on pain	T = 4.5 months (Additional call reminder for Clinical Visit #3)
Clinic Visit #3	Reapplication of SDF in that group; Assessment for major & minor failure, radiographs*, and assessment of pain and parent satisfaction	T = 6 months

Intermediate Contact	Attrition prevention, update contact information, follow-up on pain	T = 9 months (Additional call for scheduling/reminder for Clinical Visit #4)
Clinic Visit #4	Assessment for major & minor failure, radiographs*, and final questionnaires	T = 12 months

\* Radiographs will be obtained only if an existing radiograph within 30 days of the visit is not available.

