## **10. Statistical Analysis**

Power of the study will be fixed at 80% ( $\beta=0.20$ ) just as was used in calculation for necessary sample size, with  $\alpha = 0.05$  as the significance level. Data will be entered into SPSS Statistics or

another secured data collection system and data will be analyzed. Information will be stored on a password protected computer using an encrypted file and will be maintained as confidential protected health information (PHI). Examiners will be trained at the start of the study and calibrated on the use of the ICDAS criteria, and on the clinical outcome variables using extracted teeth to determine intra and inter-examiner reliability (dentin color, dentin hardness, and lesion size in mm), which will be measured with kappa statistics. A Chi-square test will be applied to determine if there is a difference in distribution of variables such as age, gender, brushing habits, fluoride exposure, etc. Chi-square tests will also be used to determine differences in dropout rates, failure rates, patient satisfaction/acceptance, and overall cost. The primary outcome, the proportion of children reporting major failures during the 12 month follow up period, will be analyzed using a mixed model with a binomial error structure. We will also analyze minor failures in a similar manner. The dependent variables will be a binary indicator of major failure, with differences between study treatments fitted as fixed effects. Estimates of the relative risk of major failure in the two groups will be presented in the form of odds ratios and associated 95% confidence intervals. Within this framework we will be able to estimate:

1. The mean difference between groups at the end of the follow up period;
2. The mean difference between groups across the whole of the follow up period; and
3. The difference in the rate of change of the outcome across the follow up period

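### Either failure type ends follow-up and hides the other, but major and minor failure are modelled separately and no any-failure analysis is defined

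*Combined protocol and SAP*

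**What the plan says.** **Follow-up.** Protocol Section 6 says: "In the event of minor or major failure in either study group, the subject will be withdrawn from the study". The tooth is then treated and put in a single failure category, with no type named. Section 4.3 allows one study tooth per child, so tooth and child are the same unit.

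**Outcome grades.** Table 2 in Section 7.2 lists success, minor failure and major failure for each arm. It does not say whether the two failure grades exclude each other.

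**Analysis.** Section 10 makes major failure over 12 months the primary outcome, as a binary indicator in a mixed model with binomial error. It continues: "We will also analyze minor failures in a similar manner". The same section lists chi-square tests for several variables, failure rates among them, without saying whether these are major, minor or combined.

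**Sizing.** Section 4.2 plans on combined failure: "the combined failure rate for conventional restorative techniques (e.g. compomers) is approximately 29% at one year follow-up", against "application of silver diamine fluoride has a failure rate of 63% at one year follow-up". This gives 34 per group. Then: "To account for 30% attrition, the final number needed for the initial study will be 98".

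**The concern.** Once the first failure of either kind ends observation, two separate yes/no outcomes no longer describe two separate risks. A tooth withdrawn with an abscess at month 3 cannot go on to record a minor failure at month 6. A tooth withdrawn with soft dentin at month 3 cannot go on to record an abscess. Each analysis needs a rule for teeth removed by the other event, and Section 10 has none.

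Two things are at stake. First, the minor-failure contrast can move in either direction according to a coding choice that the plan leaves open. Second, the primary contrast is affected too: an arm with many early minor failures has fewer teeth left in which a major failure can be seen.

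The outcome that avoids the problem, any failure, is also the one closest to the planning figures, but the plan does not define it as an analysis.

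**Working it through.** **1. The plan's own sample size.** Inputs from Section 4.2: 29% v 63%, alpha 0.05 (two-sided assumed, since the sidedness is not stated), power 80%.

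n per group = [1.96·√(2·p̄·(1−p̄)) + 0.8416·√(p1(1−p1) + p2(1−p2))]² / (p1−p2)², with p̄ = 0.46

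= [1.96·0.7048 + 0.8416·0.6626]² / 0.34² = 3.76 / 0.1156 = 32.5, so 33, against 34 stated. For 30% attrition, 34/0.70 = 48.6, so 49 per group and 98 in all, as stated. The sizing reproduces, and it belongs to combined failure.

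**2. Effect of the coding rule on minor failure.** The documents give no separate major and minor rates, so these are assumed scenarios. Take constant hazards over 12 months. Both arms have the same minor hazard, giving 30% if nothing else happened. Major failure, likewise taken alone, is 5% in arm A and 20% in arm B.

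- Hazards: minor −ln(0.70) = 0.3567; major −ln(0.95) = 0.0513 (A) and −ln(0.80) = 0.2231 (B).
- Any failure: 1 − 0.70·0.95 = 33.5% (A); 1 − 0.70·0.80 = 44.0% (B).
- Minor first = any failure × minor hazard / total hazard: 0.335·0.3567/0.4080 = 29.3% (A); 0.440·0.3567/0.5798 = 27.1% (B).
- Major first: 33.5 − 29.3 = 4.2% (A); 44.0 − 27.1 = 16.9% (B).

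| Handling of major failures | Arm A | Arm B | OR (B v A) |
|---|---|---|---|
| Coded as no minor failure | 29.3% | 27.1% | 0.90 |
| Excluded: 0.293/(1−0.042), 0.271/(1−0.169) | 30.6% | 32.6% | 1.10 |
| Any failure | 33.5% | 44.0% | – |

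With no true difference in minor hazard, the arm with more major failures looks better under the first rule and worse under the second. Over minor failure of 20–50% and major failure from 2% v 10% up to 10% v 40%, the odds ratio is 0.74–0.95 under the first rule and 1.05–1.27 under the second.

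**3. The mirror effect on the primary outcome.** Assume equal major hazards (10% alone) and minor failure of 20% v 50% alone. The major hazard is −ln(0.90) = 0.1054; the minor hazards are 0.2231 and 0.6931.

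- Major first: (1 − 0.80·0.90)·0.1054/0.3285 = 9.0%; (1 − 0.50·0.90)·0.1054/0.7985 = 7.3%. The odds ratio is 0.79, in favour of the arm with more minor failures.
- Over major 5–20% and minor 20% v 50% or 25% v 60%, the odds ratio is 0.73–0.80.

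**4. Minor-only against any failure at the planned size.** Assume that the planning totals hold and that first failures are major in 3% (conventional) and 10% or 15% (SDF). Exact chi-square power, uncorrected, 34 per arm:

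| Outcome | Conventional | SDF | Difference (points) | Power |
|---|---|---|---|---|
| Any failure | 29% | 63% | 34 | 81% |
| Minor, major coded 0 (SDF major 10%) | 26% | 53% | 27 | 65% |
| Minor, major coded 0 (SDF major 15%) | 26% | 48% | 22 | 49% |
| Minor, major excluded (SDF major 10%) | 26.8% | 58.9% | 32 | 78% |
| Minor, major excluded (SDF major 15%) | 26.8% | 56.5% | 30 | 72% |

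The excluded rates are 0.26/0.97, 0.53/0.90 and 0.48/0.85. The result depends on the split: with major failure of 5% in both arms, the minor-only rates are 24% v 58% and the difference stays at 34 points.

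**The case against.** **No coding rule is stated.** A reader might infer that the plan scores a tooth lost to abscess or extraction as free of minor failure, and so favours the arm with more major failures. The documents do not say this. Section 6 says only that such teeth count as failures. Coding them as 0 is the natural reading of a yes/no indicator taken as a proportion of children, but exclusion is open too, and the bias then reverses. This removes any claim about a known direction. It leaves the gap.

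**The two grades may overlap.** Table 2 does not make them exclusive, and a tooth seen with an abscess at a visit may also show soft dentin at that visit. Section 4.4 says that a provider can withdraw a failing patient, while Section 6 says that the subject will be withdrawn. Both points stand. They add undefined cases, and the two sections must be reconciled.

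**A combined test may already be intended.** The chi-square test on failure rates, read with the single failure category in Section 6, could be an any-failure comparison. It would be wrong to say that the plan excludes one. But the test is undefined, and no model is attached to it.

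**The power figures do not measure bias.** This is correct. Step 4 compares different endpoints under assumed splits, and with exclusion the loss is small. It shows only what minor failure alone leaves out.

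**A separate minor-failure result is legitimate description.** This also stands: reported beside major failure it is informative, and it need not be deleted.

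**Conclusion.** The concern holds in this form: each failure type is a competing event for the other, Section 10 has no rule for it, and the outcome closest to the sizing has no defined analysis. The gap affects the primary major-failure outcome as well as minor failure.

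The size cannot be fixed from the documents, which give no major/minor split. The SDF planning figure of 63% is the complement of the 37% arrest at 12 months cited in Section 3.5, so it does not show how much would be major failure. In the assumed scenarios, spurious minor-failure odds ratios run from 0.74 to 0.95 under one coding and from 1.05 to 1.27 under the other. Spurious major-failure odds ratios run from 0.73 to 0.80. These rest on constant, independent hazards. The distortion in minor failure is modest unless major failures are frequent and differ between arms.

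The sponsor should settle this before the data are analysed.

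**What to change.** In Section 10:

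1. Specify any failure (minor or major, first occurrence) by 12 months as a defined analysis, in the same model as the primary outcome, and define the chi-square test on failure rates as this outcome.
2. Report the minor/major split by arm, either descriptively or as the ordered outcome success/minor/major. Say which grade is counted when a tooth meets both definitions at one visit. Do not interpret minor failure on its own as a treatment effect.
3. State that the major-failure results count first failures only, because follow-up stops at a minor failure.

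Sections 4.4 and 6 should also be reconciled on withdrawal after failure, so that the analysis rule matches what was done.

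The cost is wording: the Table 2 assessments at 3, 6 and 12 months already supply the data. The downside is that a stand-alone p-value for minor failure carries less weight.

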#### **4.4. Participant Allocation and Blinding**

Subjects enrolled in the study will be randomly assigned to one of the two caries management groups in a 1:1 ratio. Although treatment will be randomly assigned, it will not be possible to blind parents, children, or dentists to the assigned treatment group as the post-operative appearance is likely to differ markedly between groups. In the event treatment for the patient is failing, regardless of the treatment arm assigned, the provider will recommend additional treatment and can withdraw the patient at any time and appropriate reasoning will be recorded. Patients/parents have the right to withdraw from the study at any time and for any reason as well. Additionally their reasoning for withdrawal will be recorded (Appendix 10, CRF 04, 11, 14-17).

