### 7.2. Clinical Variables

At the baseline visit the study teeth carious lesions will be assessed based on size (mm), dentin color (yellow, brown, black), dentin hardness (soft - any explorer penetration of dentin when very light force is applied or hard – no dentin penetration when using an explorer with very light force), and periapical radiographs (outer/middle/inner third of dentin, major/minor failure criteria). All information will be noted on the respective *CRF Intervention Visit* by the provider prior to treatment. These clinical characteristics will also be recorded for the SDF groups at follow-up visits (as the lesion is exposed clinically). Recall clinical visits will involve assessment of the lesion based on minor and major failure criteria (Table 2). All assessments will be noted on the respective *CRF 3 & 6 Month* (Appendix 10, CRF 10 & 11) or on the *CRF 12 Month* at the patient's 12 month recall (Appendix 10, CRF 12 & 13). Both groups will have periapical radiographs taken at the baseline and 6 and 12 month recalls (and at any other time if deemed clinically necessary). If a radiograph from within 30 days of the visit is available, a radiograph will not be taken at the study visit unless deemed clinically necessary. De-identified clinical photos will also be taken as deemed necessary for research and publication purposes, with parental consent. Length of time and cost for each intervention will be calculated and analyzed for comparison.

**Table 2.** Major and Minor Failure Criteria

	SDF Application	Conventional Restoration
Success	
 
• Caries arrested – dentin feels hard to explorer
 
• No clinical signs or symptoms of pulpal pathology
 
• Tooth exfoliated without major or minor failure
 
	
 
• Restoration appears satisfactory
 
• No clinical signs or symptoms of pulpal pathology
 
• Tooth exfoliated without major or minor failure
 

Minor Failure	
 
• Caries progression – soft dentin, increase in lesion size clinically or radiographically
 
• Reversible pulpitis to be treated without pulpotomy or extraction
 
	
 
• Secondary caries
 
• Restoration fracture or wear requiring repair
 
• Loss of restoration
 
• Reversible pulpitis to be treated without pulpotomy or extraction
 

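### The primary model names no site or baseline lesion covariate and no site stratification is described, which gives up a modest amount of precision that could be recovered almost free

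*Combined protocol and SAP*

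**What the plan says.** - **Model.** Section 10 analyses major failure over 12 months with a binomial mixed model, "with differences between study treatments fitted as fixed effects", and treats minor failure in the same way. It names no other fixed effect and no random effect. It lists three estimates: the group difference at the end of follow-up, the difference across follow-up, and the difference in rate of change.
- **Baseline comparisons.** The same section applies chi-square tests to variables such as age, gender, brushing and fluoride exposure. No adjustment follows from the result, and neither site nor any lesion measure is among the examples.
- **Allocation.** Section 4.4 says that children are "randomly assigned to one of the two caries management groups in a 1:1 ratio". It mentions no list type, blocks or strata.
- **Sites.** Section 4.2 says that, after slow recruitment, the university clinic "was added as a second study site". Section 11 expects five or six residents at each site and calls the number of providers a limitation.
- **Baseline lesion data.** Section 7.2 records lesion size, dentin colour, dentin hardness and "periapical radiographs (outer/middle/inner third of dentin, major/minor failure criteria") before treatment.

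**The concern.** Site brings its own operators and patients, and because the second site opened later it is also tied to calendar time. A deeper or larger lesion may be more likely to fail under either treatment. If these factors predict failure, leaving them out of both the allocation and the model has two costs. The comparison is less precise than the collected data allow, and a chance difference between arms stays in the primary estimate. A chi-square table can reveal such a difference but cannot remove it.

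There is also a prespecification problem. Treatment cannot be blinded in this trial. If an imbalance appears and nothing was fixed in advance, adjustment would be chosen with the arms visible, and the choice could be disputed.

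**Working it through.** **1. The plan's own figure.** Inputs from section 4.2: "the combined failure rate for conventional restorative techniques (e.g. compomers) is approximately 29% at one year follow-up", "application of silver diamine fluoride has a failure rate of 63% at one year follow-up", and an alpha "value of 0.05 and a Power set at 80" percent. Sidedness is not stated, so two-sided is used here. With pooled variance and no continuity correction, and a mean rate of 0.46:

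n = [1.960·√(2 × 0.46 × 0.54) + 0.8416·√(0.29 × 0.71 + 0.63 × 0.37)]² / 0.34² = (1.3815 + 0.5576)² / 0.1156 = 32.5, so 33 per arm against the stated 34.

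One-sided gives 26 per arm, so the two-sided reading fits. At 34 per arm, z = (0.34 × √34 − 1.3815) / 0.6626 = 0.907, which is power of 81.8%. Attrition: 34/0.70 = 48.6, so 49 per arm and 98 in total, as stated.

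**2. What adjustment adds.** The documents give no prognostic strength, so a range is assumed: one standardised baseline score with an odds ratio (OR) of 1 to 3 per SD, and marginal failure rates held fixed. Logistic likelihood-ratio tests, 34 per arm, 4,000 runs per row (simulation standard error about 0.6 points near 82%):

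| Failure rates | OR per SD | Unadjusted power | Adjusted power | Gain (points) |
|---|---|---|---|---|
| 29% vs 63% | 1 | 82.6% | 82.5% | none |
| 29% vs 63% | 1.5 | 82.3% | 83.0% | 0.7 |
| 29% vs 63% | 2 | 82.2% | 85.7% | 3.5 |
| 29% vs 63% | 3 | 83.1% | 89.7% | 6.6 |
| 5% vs 20% | 1 | 51.8% | 51.9% | none |
| 5% vs 20% | 1.5 | 52.0% | 53.0% | 1.1 |
| 5% vs 20% | 2 | 51.8% | 54.7% | 2.9 |
| 5% vs 20% | 3 | 52.1% | 57.8% | 5.8 |

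The 5% vs 20% rows matter because the primary outcome is major failure, whereas 29% and 63% are overall failure rates. Those two major-failure rates are assumptions.

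A second structure was tried: site (OR 2) plus one binary lesion covariate. At 29% vs 63%, power rises from about 82–83% to 86% (lesion OR 3) or 88% (OR 5); an OR of 8, which is extreme, gives 89–90%. At 5% vs 20% with lesion OR 3, it goes only from 50.5% to 51.4%.

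**3. Validity.** At 29% in both arms, unadjusted type I error is 5.2–5.3%, and 5.2–5.8% with adjustment. At 5% in both arms, the likelihood-ratio test rejects 8–9% of the time with or without the covariate. That comes from sparse events, not from omitted covariates, and it makes the 5% vs 20% power figures optimistic.

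**4. Chance imbalance in site.** Hypergeometric, 98 children, 49 per arm, no stratification. With 49 children at each site, the arms differ by at least 10 points (for example 27 vs 22) in 41.9% of allocations, by 15 or more in 10.6%, and by 20 or more in 4.3%. For a smaller second site the 10-point figure depends on its exact size: 24.0%, 35.4%, 28.1% and 39.3% for 24, 25, 32 and 33 children.

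**5. What such an imbalance does.** Assume equal sites and a site OR of 2. Site-specific failure is then 22.0% and 36.0% (mean 29%) in one arm and 55.0% and 71.0% (mean 63%) in the other. A 55:45 versus 45:55 site mix moves the risk difference by 0.05 × 14.1 + 0.05 × 16.0 = 1.5 points out of 34. At 5% vs 20% the site gaps are 3.2 and 10.9 points, and the shift is 0.05 × (3.2 + 10.9) = 0.7 points out of 15.

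**The case against.** The strongest reply is that little is lost. Randomisation already allows for chance imbalance in the test, the planned number gives about 82% power unadjusted at its own rates, and a 10-point site imbalance moves the estimate by 1.5 points or less under a site odds ratio of 2. No passage shows that depth, size or site predicts failure. For major failure, the gain could be a single point. All of this stands, and it limits the point to efficiency and prespecification.

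A reader might also infer three stronger things that the documents do not support:

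- **That allocation used a simple unstratified list.** Section 4.4 does not describe the method. Stratification is unreported, not ruled out, and the imbalance figures apply only if there was none.
- **That the model contains treatment alone.** It is a mixed model with unnamed random effects, and the three listed estimates imply time and treatment-by-time terms. A site or provider random effect is not excluded. What can be said is that no site or baseline covariate is named.
- **That every recorded measure would help.** Eligibility requires soft lesions, so baseline hardness can hardly vary. Number of surfaces is an entry condition and is not among the measures listed in section 7.2. Size and radiographic depth are the usable candidates. Site would not capture differences among the residents within a clinic.

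**Conclusion.** The point holds as an improvement, not as a flaw that invalidates the analysis. The plan names neither site nor a lesion measure in the model, describes no stratification by site, and has no step that acts on a baseline imbalance. At the planned rates the test keeps its error rate.

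The loss is roughly 1 to 7 power points at 29% vs 63% and about 1 to 6 at 5% vs 20%, for odds ratios of 1.5 to 3 per SD, and zero if the covariate is not prognostic. The odds ratios and the major-failure rates are assumptions, so the range is indicative only.

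It should not be read as a remedy for low power on major failure. By the formula in step 1, 34 per arm gives about 46% power at 5% vs 20%, and covariate adjustment would not repair that.

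**What to change.** Before outcomes are compared between arms:

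1. Prespecify site and one baseline lesion measure (radiographic depth third or size) as fixed effects in both the major-failure and minor-failure models. State the random effects and time terms in the same place.
2. Prespecify penalised likelihood if major failures are few.
3. Report a standardised risk difference beside the adjusted odds ratio.
4. State how the allocation sequence was generated and whether it was stratified by site. If enrolment is still open, which the documents do not settle, use separate permuted-block lists per site from now on.

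The cost is SAP wording and possibly a second list, with no extra patients or data collection. There are two small downsides. The adjusted odds ratio is conditional on the covariates, so it differs in meaning from the unadjusted one, which is why the risk difference should accompany it. Few major failures also limit how many covariates the model can carry, hence one lesion measure and not several.

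### Section 10 calls an odds ratio a relative risk, and promises whole-period and rate-of-change contrasts without the model terms or the rule for failed children that they need

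*Combined protocol and SAP*

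**What the plan says.** All of the analysis text is in Section 10 (Statistical Analysis) of the combined protocol and SAP. The primary outcome is "the proportion of children reporting major failures during the 12 month follow up period", and it "will be analyzed using a mixed model with a binomial error structure", "with differences between study treatments fitted as fixed effects". No time term, treatment-by-time term or random effect is named. On the effect measure it says: "Estimates of the relative risk of major failure in the two groups will be presented in the form of odds ratios", with 95% confidence intervals. It adds: "We will also analyze minor failures in a similar manner".

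Section 10 then lists three contrasts that this framework is to yield:

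1. how far apart the arms are, on average, when follow-up ends
2. an average over all visits, worded as "The mean difference between groups across the whole of the follow up period"
3. how the arms differ in the speed at which the outcome changes over follow-up

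Section 6 (Study Visits and Intermediate Contacts) sets clinic visits at 3, 6 and 12 months. It withdraws a child, in either arm, when the study tooth has a minor or a major failure, and counts that tooth as failed. Section 4.3 allows one study tooth per child.

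**The concern.** Three parts of the plan do not fit together.

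- **Effect measure.** The sentence on relative risk names one quantity and delivers another. If failure is common, a reader who takes the odds ratio as the relative risk will overstate the difference between arms.
- **Model and contrasts.** A rate-of-change contrast cannot come from a model whose only fixed effect is treatment. A whole-period contrast needs visit-level records and a stated way of combining them.
- **Failure ends follow-up.** Once a child is withdrawn, there are no later visits. Section 10 does not say whether failed status is carried forward or the child leaves the risk set. Two analysts could choose differently, both follow the text, and report different results. Separately, a child withdrawn at minor failure can no longer be seen to have a major failure, which is the primary outcome.

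**Working it through.** **Inputs.** Section 4.2 gives a 29% combined failure rate for conventional restorations and a 63% failure rate for SDF at one year, 34 per group, and 98 enrolled after 30% attrition. Section 3.5 shows that 63% is the complement of 37% caries arrest with annual application; biannual application gave 53% arrest, hence 47%. None of these is a major-failure rate, and the documents give none.

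**Plan's own figure.** A two-sided two-proportion calculation (pooled variance, no continuity correction) at 29% vs 63% gives 33 per group, against 34 stated. For attrition, 34/0.70 = 48.6, rounded up to 49 per arm, or 98. The sample size reproduces and is not at issue.

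**Odds ratio against risk ratio, common outcome (size only).** With RR = p2/p1 and OR = [p2/(1-p2)]/[p1/(1-p1)]:

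- 29% vs 63%: RR = 0.63/0.29 = 2.17; OR = (0.63/0.37)/(0.29/0.71) = 4.17; risk difference 34 points.
- 29% vs 47%: RR = 0.47/0.29 = 1.62; OR = (0.47/0.53)/(0.29/0.71) = 2.17; risk difference 18 points.

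With 34 per arm, log-scale Wald 95% intervals for the 29% vs 63% case are 1.21 to 3.90 for the RR and 1.51 to 11.52 for the OR.

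**Odds ratio against risk ratio, rarer outcome (assumed control risk c, other arm RR x c).** The two RRs are borrowed from the lines above, for illustration only.

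| Assumed c | OR when RR is 2.17 | OR when RR is 1.62 |
|---|---|---|
| 2% | 2.23 | 1.64 |
| 5% | 2.32 | 1.68 |
| 10% | 2.50 | 1.74 |

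**Effect of the missing rule on contrasts 2 and 3.** Assume constant hazards that reach 29% and 63% at 12 months, with visits at 3, 6 and 12 months. This illustrates failure of any kind, not major failure. Cumulative risk at month t is 1-(1-p)^(t/12), which gives 8.2%, 15.7% and 29.0% against 22.0%, 39.2% and 63.0%.

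- *Failure carried forward.* Visit odds ratios are 3.16, 3.45 and 4.17. Risk differences are 13.8, 23.4 and 34.0 points, mean 23.7.
- *Failed children leave the risk set.* Risks per interval are 8.2%, 8.2% and 15.7% against 22.0%, 22.0% and 39.2%. Visit odds ratios are 3.16, 3.16 and 3.45. Risk differences are 13.8, 13.8 and 23.4 points, mean 17.0.

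The same data thus give a whole-period difference of 23.7 or 17.0 points and a different trend in the odds ratio. The hazards are constant here, so the trend reflects only the coding rule and the longer last interval.

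**Withdrawal at minor failure.** If an arm of n children has m observed major failures and w withdrawals at minor failure, its 12-month major-failure risk lies between m/n and (m+w)/n. The width w/n cannot be put in figures, because the documents give no minor-failure rate.

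**Separate sparse-data note (assumed risks).** The chance that at least one arm has no major failure is 1-[1-(1-c)^n][1-(1-t)^n], with t = RR x c. At c = 2%, 5% and 10% with n = 34, it is 61%, 19% and 3% for RR 2.17, and 67%, 22% and 3% for RR 1.62. With n = 49, it is 44%, 8% and 1%, or 50%, 10% and 1%. An arm with no events breaks the usual risk ratio and odds ratio alike, so this does not bear on the choice between them.

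**The case against.** An odds ratio is a normal output of a binomial model, and the plan says that is what will be presented, so the published figure would carry its right name. For major failure the gap is small if the risk is low, and small beside the sampling error with 34 per arm. This stands, and it limits the labelling point. It does not make the sentence correct, and the same approach is applied to minor failure, which may be common.

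A mixed model is not odd merely because each child has one tooth: there are three assessment visits, two sites, and five or six residents treating at each site (Section 11). This stands too; the gap is that the terms are not named. Nor need the mean difference in the list of contrasts be a third effect measure, since it could be meant on the logit scale. The wording is unclear rather than shown to conflict.

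A reader might infer two stronger points. One is that the primary odds ratio would be about twice the risk ratio. The documents do not support this, because 29% and 63% are combined-failure or non-arrest rates. The other is that a child with major failure has no defined place in the primary outcome. Section 6 counts that tooth as failed and the outcome is cumulative over 12 months, so the child is settled there. What stays open is the child's part in contrasts 2 and 3, and any major failure after withdrawal at minor failure.

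**Conclusion.** The concern holds in a limited form, and Section 10 should be corrected before analysis. The stated measure is not the stated quantity, and the stated model cannot give the rate-of-change contrast. For major failure the labelling gap is probably modest: OR 2.23 to 2.50 for an RR of 2.17 at assumed control risks of 2% to 10%. For an outcome as common as the planning rates it would be large (4.17 against 2.17). The choice of rule for failed children moves the whole-period difference from 23.7 to 17.0 points under the constant-hazard assumption; the true size depends on failure rates by visit, which the documents do not give. Nothing shows that contrasts 2 and 3 are more than supportive. The loss of later major failures after minor-failure withdrawal does touch the primary outcome, but its size is unknown.

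**What to change.** - **Primary result.** Report each arm's 12-month major-failure risk, with the risk difference and risk ratio and 95% confidence intervals. If events are few or an arm has none, use exact, score or Firth methods. Label any odds ratio as an odds ratio. Treat minor failure the same way.
- **Contrasts 2 and 3.** Either use a discrete-time survival analysis over the 3, 6 and 12 month visits, or state that failure is carried forward and name the time and treatment-by-time terms and the random terms (for example child, site or provider). State the scale of each contrast.
- **Children withdrawn at minor failure.** Do not rely on coding them as free of major failure: if minor failure differs by arm, that coding favours the arm with more of it. Report any failure, minor or major, by arm. Bound the major-failure result by coding these children as none failed and as all failed. The widest bounds on the between-arm difference come from using opposite codings in the two arms.

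The cost is rewording Section 10 and a little more analysis work in standard software. No new data are needed, and the sample size and the withdrawal rule stay as they are.
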